## 1. ABBREVIATIONS AND DEFINITION OF TERMS

ACR	American College of Rheumatology
ADL	Activities of daily living
ADaM	Analysis Data Model
ADP	average daily pain
ADRG	Analysis Data Reviewer's Guide
AE	adverse event
ANOVA	analysis of variance
AUC	area under the concentration-time curve
BMI	Body Mass Index
CDISC	Clinical Data Interchange Standards Consortium
CFR	Code of Federal Regulations
CGIC	Clinical Global Impression of Change
CI	confidence interval
CMC	Carboxymethylcellulose sodium
CTCAE	Common Terminology Criteria for AEs
CSR	Clinical Study Report
CV	coefficient of variation
ECG	Electrocardiogram
eCRF	electronic case report form
EDC	electronic data capture
EULAR	European League Against Rheumatism
GCP	Good Clinical Practice
GPAQ	Global Physical Activity Questionnaire
HIV	Human Immunodeficiency Virus
HPA	hypothalamic-pituitary-adrenal
IA	intra-articular
IB	Investigator's Brochure
IRB/EC	Institutional Review Board/Ethics Committee
IM	intramuscular
IV	intravenous
K-L	Kellgren-Lawrence
KM	Kaplan-Meier
KOOS	Knee injury and Osteoarthritis Outcome Score
MedDRA	Medical Dictionary for Regulatory Activities
MMRM	mixed model for repeated measures
NaCl	sodium chloride
OA	osteoarthritis

OARSI	Osteoarthritis Research Society International
PGIC	Patients' Global Impression of Change
PLGA	poly[lactic-co-glycolic acid]
PK	pharmacokinetic
PRP	platelet rich plasma
PTOA	post-traumatic osteoarthritis
QOL	Quality of Life
QTc	QT interval corrected for heart rate
RBC	red blood cells
SAE	serious adverse event
SAP	statistical analysis plan
SDRG	Study Data Reviewer's Guide
SDTM	Study Data Tabulation Model
TEAE	treatment-emergent adverse event
TA 	triamcinolone acetonide
TAcS 	triamcinolone acetonide injectable suspension, immediate-release (commercially available)
US	United States
USP	United States Pharmacopeia
w/w	weight/weight
WBC	white blood cells
WOMAC	Western Ontario and McMaster Universities Osteoarthritis Index

 Abbreviated in past protocols and documents as TCA

 Abbreviated in past protocols and documents as TCA-IR

## 2. SYNOPSIS

Title of Study: An Open-label Study to Assess the Safety of Repeat Administration of FX006 to Patients with Osteoarthritis of the Knee
Study Centers: Approximately 20 centers
Study Phase: 3b
Objectives: The primary objective of this study is to assess the overall safety and general tolerability of repeat administration of FX006 (two doses of 32 mg FX006) in patients with symptomatic osteoarthritis (OA) of the knee. Exploratory objectives of this study include the following: 

• examine efficacy signals for sustained pain reduction following two doses of 32 mg FX006.

• collect synovial fluid samples to enable potential future examination of synovial fluid biomarkers that may contribute to the pathogenesis of OA and/or be associated with responsiveness to FX006 treatment.

Study Design and Methodology: This study is an open-label, repeat administration design of 32 mg FX006. The study will be conducted in male and female patients $\geq$ 40 years of age with symptomatic OA of the knee. Eligible patients will be offered participation to receive an initial IA injection of FX006 administered to the index knee at Day 1. Patients who receive an initial injection of FX006 will return at Weeks 4 and 8 before being evaluated at 12, 16, 20, and 24 weeks following the initial administration of FX006 for repeat administration. At the first visit where the patient has been determined to meet repeat administration eligibility criteria described in Section 7.4.3, the patient will be eligible to receive a second IA injection of FX006 administered to the index knee. Patients who are eligible to receive a second injection will be evaluated for a total of 52 weeks post initial injection at: Weeks 4, 8, 12, 16, 20, 24, 28, 32, 36, 40, 44, 48, and 52, regardless of the visit at which they receive their second injection. Patients that do not benefit from the initial treatment as determined by evaluation at Week 12 will complete the study at the Week 12 follow-up visit. These patients will be evaluated for a total of 12 weeks post initial injection at: Weeks 4, 8, 12. Patients who are not eligible for a second injection of FX006 after evaluation at Weeks 12, 16, 20, and 24 will complete the study at the Week 24 follow-up visit. These patients will be evaluated for a total of 24 weeks post initial injection at: Weeks 4, 8, 12, 16, 20, and 24. Refer to Appendix 2 Study Visit Flow Chart . The study is expected to enroll over approximately 6 months.
Number of Patients: Approximately 200 patients will be enrolled to ensure that at least 100 patients receive two doses of 32 mg FX006 and complete the study through Week 52.
Test Product, Dose and Mode of Administration: FX006 – extended release formulation of TA in 75:25 poly(lactic-co-glycolic) acid (PLGA) microspheres. Nominal 32 mg TA, IA, administered as a single 5 mL injection
Reference Compound(s), Dose and Mode of Administration: Not applicable

**Duration of Dosing:**

Single IA injection for all enrolled patients at Day 1/Baseline, and a second IA injection for those meeting repeat administration requirements at either Week 12, 16, 20, or 24.

**Screening Inclusion Criteria:**

To be included in the trial, patients must fulfill the following criteria to participate in the study

1. Written consent to participate in the study
2. Willingness and ability to comply with the study procedures and visit schedules and ability to follow verbal and written instructions
3. Male or female  $\geq 40$  years of age
4. Symptoms associated with OA of the index knee for  $\geq 6$  months prior to Screening (patient self-report is acceptable)
5. Currently meets ACR Criteria (clinical and radiological) for OA ([Altman et al, 1986](#)) as follows:
  - Knee pain
  - at least 1 of the following:
    - Age  $> 50$  years
    - Stiffness  $< 30$  minutes
    - Crepitus
  - Osteophytes
6. Kellgren-Lawrence (KL) Grade 2, 3 or 4 in the index knee based on X-ray performed during Screening (locally read)
7. WOMAC A total sum score of  $\geq 6$  at Screening and Day 1/Baseline
8. Index knee pain for  $>15$  days over the last month (as reported by the patient)
9. If bilateral OA exists, pain in the contralateral knee must be less than pain in the index knee as reported by the patient
10. Body mass index (BMI)  $\leq 40 \text{ kg/m}^2$
11. Ambulatory and in good general health
12. Willingness to abstain from use of the following protocol-restricted medications during the study:
  - Intravenous (IV), intramuscular (IM) and oral corticosteroids (Note: inhaled, intranasal and topical corticosteroids are allowed)
  - IA corticosteroids in any joint
  - IA viscosupplementation (hyaluronic acid) or any IA intervention (IA injection, IA aspiration, etc.) in the index knee
  - Opiates
  - Any investigational drug, device or biologic
  - Immunomodulators, immunosuppressives, or chemotherapeutic agents
  - Live or live attenuated vaccines

**Screening Exclusion Criteria:**

Patients fulfilling at least one of the following criteria may not be included in the study:

**Disease-related criteria**

1. Reactive arthritis, rheumatoid arthritis, psoriatic arthritis, ankylosing spondylitis, or arthritis associated with inflammatory bowel disease
2. History of infection in the index knee joint
3. Clinical signs and symptoms of active knee infection or crystal disease of the index knee within 1 month of Screening
4. Presence of surgical hardware or other foreign body in the index knee
5. Unstable index knee joint (such as a torn anterior cruciate ligament) within 12 months of Screening

**Previous or concomitant treatment-related criteria**

6. IA corticosteroid (investigational or marketed) in index knee within 3 months of Screening
7. IA hyaluronic acid (investigational or marketed) in the index knee within 6 months of Screening
8. IV or IM corticosteroids (investigational or marketed) within 3 months of Screening
9. Oral corticosteroids (investigational or marketed) within 1 month of Screening
10. Any other IA drug/biologic use within 6 months of Screening or 5 half-lives (whichever is longer) (e.g., platelet rich plasma (PRP) injection, stem cells, prolotherapy and amniotic fluid injection)
11. Prior administration of FX006
12. Prior arthroscopic or open surgery of the index knee within 12 months of Screening
13. Planned/anticipated surgery of the index knee during the study period

**Patient-related criteria**

14. Known hypersensitivity to any form of triamcinolone
15. History of sarcoidosis or amyloidosis
16. Active or history of malignancy within the last 5 years, with the exception of resected basal cell carcinoma, squamous cell carcinoma of the skin, or effectively managed cervical carcinoma
17. Known active or quiescent systemic fungal, bacterial, mycobacterial (including tuberculosis), viral or parasitic infections, or, shingles, herpes zoster and ocular herpes simplex
18. Any infection requiring IV antibiotics within 4 weeks of Screening or oral antibiotics within 2 weeks of Screening
19. History of osteomyelitis
20. Known or clinically suspected infection with human immunodeficiency virus (HIV), hepatitis B or C viruses
21. Any clinically significant electrocardiogram (ECG) abnormality as judged by the Investigator
22. Patients requiring or likely to require chronic treatment with corticosteroids during the study period based on patient medical history
23. History of, or active Cushing's syndrome
24. Active substance abuse (drugs or alcohol), history of chronic substance abuse within the past year, or prior chronic substance abuse judged by the investigator as likely to recur during the study
25. Skin breakdown at the knee where the injection would take place
26. Women who are pregnant or nursing or plan to become pregnant during the study; men who plan to conceive during the study
27. Women of child-bearing potential (not surgically sterile or post-menopausal for at least 1 year as documented in medical history) not using a highly effective method of contraception [abstinence; oral, injected or implanted hormonal methods of contraception; intrauterine device or intrauterine system; condom or occlusive cap (diaphragm or cervical/vault caps) with spermicidal foam/gel/film/cream/suppository; or male sterilization (vasectomy)]

28. Use of immunomodulators, immunosuppressives, or chemotherapeutic agents within 5 years of Screening
29. Has received a live or live attenuated vaccine within 3 months of Screening
30. Use of any other investigational drug or device within 30 days of Screening or within 5 half-lives (whichever is longer) or an investigational biologic within 60 days of Screening or within 5 half-lives (whichever is longer)
31. Any other clinically significant acute or chronic medical conditions (e.g., bleeding disorder) that, in the judgment of the Investigator, would preclude the use of an IA corticosteroid or that could compromise patient safety, limit the patient's ability to complete the study, and/or compromise the objectives of the study

**Repeat Administration Inclusion Criteria:**

To be eligible to receive a repeat administration, patients must fulfill the following criteria:

1. Benefit from the initial dose of FX006 in the opinion of both the patient and the Investigator
2. No major safety concerns during the initial dose period as assessed by the Investigator
3. Clinically indicated to receive a second dose of FX006 in the opinion of both the patient and the Investigator
4. WOMAC A total sum score of  $\geq 6$  or a clinical rationale as to why a second dose is indicated
5. Compliant with study procedures and visit schedules through at least Week 12 and the willingness and ability to continue to comply through Week 52
6. Willingness to abstain from use of protocol-restricted medications during the study

**Repeat Administration Exclusion Criteria:**

Patients fulfilling at least one of the following are not eligible to receive a repeat administration:

1. Clinical signs and symptoms of active knee infection or crystal disease of the index knee
2. Received a non-protocol specified IA intervention (IA injection, IA aspiration, etc.) in index knee during study participation
3. Use of immunomodulators, immunosuppressives, or chemotherapeutic agents during study participation
4. Received a live or attenuated vaccine during study participation
5. Use of any other investigational drug, device or biologic during study participation
6. Allergic reaction to initial dose of 32 mg FX006
7. Any infection requiring IV antibiotics within 4 weeks or oral antibiotics within 2 weeks of second dose of FX006
8. Skin breakdown at the knee where the injection would take place
9. Women who are pregnant or nursing or plan to become pregnant during the study; men who plan to conceive during the study
10. Women of child-bearing potential (not surgically sterile or post-menopausal for at least 1 year as documented in medical history) not using a highly effective method of contraception [abstinence; oral, injected or implanted hormonal methods of contraception; intrauterine device or intrauterine system; condom or occlusive cap (diaphragm or cervical/vault caps) with spermicidal foam/gel/film/cream/suppository; or male sterilization (vasectomy)]
11. Any other clinically significant acute or chronic medical conditions (e.g., bleeding disorder) that, in the judgment of the Investigator, would preclude the use of an IA corticosteroid or that could compromise patient safety, limit the patient's ability to complete the study, and/or compromise the objectives of the study

**Procedures and Assessments:**

The study will involve a Screening period (a minimum of 7 days, up to 21 days), dosing at Day 1/Baseline and up to 13 additional outpatient visits (Weeks 4, 8, 12, 16, 20, 24, 28, 32, 36, 40, 44, 48, and 52) depending if the patient is eligible for and receives a second injection.

At specified times throughout the study, patients will undergo physical examinations, index knee assessments and index knee X-rays; blood samples will be collected for laboratory safety tests and vital signs will be collected or measured. Information regarding AEs and concomitant medications will be collected.

Patients will have index knee synovial fluid collected at baseline and the week at which the second dose is administered (if the patient is eligible to receive a second dose). Patients that are not eligible to receive a second dose will not have synovial fluid drawn at their final study visit. These samples will be preserved for potential future OA biomarker analyses.

Steps per day will be captured using a measured function device. Patients will be provided with a device at the Screening visit to be worn for at least 7 days prior to Baseline/Day 1 through Week 12. The site will confirm patient compliance with wearing the device to capture steps per day data at each patient visit from Day 1 through Week 12. As well, patients will complete the Global Physical Activity Questionnaire (GPAQ) at Screening and at Week 12.

During out-patient visits, patients will complete the Western Ontario and McMaster Universities (WOMAC®) Osteoarthritis Index Likert (LK) 3.1 and the Knee injury and Osteoarthritis Outcome Score (KOOS) Quality of Life (QOL) Subscale.

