#### **4.2.8. Missing, Unused, and Spurious Data**

For WOMAC, the rules as described in the WOMAC user guide (Bellamy 2011) will be used. Specifically, if at least 2 pain, both stiffness, or at least 4 function items are missing, the patient's response will be regarded as invalid and the score for that given subscale as well as the total score will be left missing. If no more than 1 pain, 1 stiffness, and less than 4 function items are missing, the missing value in a given subscale will be imputed using the average of all items in the given subscale. Imputed WOMAC scores will be flagged in the data listings.

---

 Copyright 2015, SAS Institute Inc. SAS and all other SAS Institute Inc. product or service names are registered trademarks or trademarks of SAS Institute Inc., Cary, NC, USA.

For the KOOS QOL subscale, the rules as described in KOOS Scoring 2012 (<http://www.koos.nu/>) will be used. Specifically, the score is only calculated if at least 2 items are non-missing. Otherwise the score will be set to missing.

For calculating weekly mean steps per day using Fitbit data, patients need to have at least 3 of 7 daily values in a given week to provide a robust assessment of activity. The denominator used for calculating means will be the total number of days in which steps per day is non-missing.

To be included in the GPAQ analyses, there must be a valid response for at least one domain and no invalid responses for any domains.

Other than for the WOMAC and KOOS QOL, missing data will not be imputed and will be analyzed "as observed".

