#### 4.2.9. Visit Windows

All data listings that contain an evaluation date will contain a relative study day (Rel Day Dose 1). Pre-treatment and post-treatment study days are numbered relative to the day of the first dose of study treatment, which is designated as Day 1. The preceding day is Day -1, the day before that is Day -2, etc. Listings will also contain a study day (Rel Day Dose 2) relative to the second dose of study treatment, which is designated as Day 1. For patients that do not receive a second dose, Rel Day Dose 2 will be "NA". For Rel Day Dose 2, preceding days (e.g., Day -1, -2) will not be derived or presented. In other words, if the date is prior to Dose 2, only Rel Day Dose 1 will be presented. If the date is after Dose 2, then both Rel Day Dose 1 and Rel Day Dose 2 will be presented.

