#### **4.9.3. Daily activity measured as steps per day**

Steps per day data are collected from baseline to Week 12, so analysis only applies to a single injection of FX006. Weekly mean steps per day from Fitbit data will be calculated for baseline through Week 12 using the visit windows presented in section 4.2.9. Values of <1000 will be set to missing since they were considered invalid upon review of the data. Handling of missing data is presented in section 4.2.8.

A cumulative activity score will be calculated for each patient, defined as the incremental sum of the weekly average between Weeks 1 and 12. Incremental sum of weekly mean steps per day will be calculated as follows:

- Incremental sum (Week 1) = Weekly mean steps per day (Week 1)
- Incremental sum (Week 2) = Incremental sum (Week 1) + Weekly mean steps per day (Week 2)
- Incremental sum (Week x) = Incremental sum (x-1) + Weekly mean steps per day (Week x)

Descriptive statistics will include number of observations, unadjusted mean, standard deviation, median, minimum and maximum values by week. Values presented will be actual weekly mean steps per day, change from baseline in weekly mean steps per day, and incremental sum of weekly mean steps per day. A line plot will present each of these values by week.

A responder analysis will be performed in the same way that is described in section 4.9.1.3. Steps per day (Fitbit) responders are defined as patients who have  $\geq 10\%$  increase in weekly mean steps per day from baseline at a given visit.

The correlation between change from baseline in steps per day and change from baseline in WOMAC A, B, C and total score and the KOOS QOL subscale at Week 4, Week 8 and Week 12 will be explored. Pearson correlation will be used if both parameters are normally distributed. Spearman correlation will be used if either parameter is not normally distributed. The mean and median values for each parameter and the correlation coefficient will be presented in a table. Change from baseline for WOMAC A, B, C and total score and the KOOS QOL subscale versus change from baseline for average steps per day at Week 4, Week 8 and Week 12 will be presented in scatter plots, which will also include a best fit line.

A data listing will present steps per day for each patient as well as number of days that contributed to each weekly average and the number that were missing.

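### When Screening lasts exactly 7 days, the step-count baseline includes the part-day on which the device was issued, which biases the baseline low in those patients only

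*Protocol*

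**What the plan says.** - **Device issue.** Protocol Synopsis, Procedures and Assessments (repeated in section 7.9.11 and Table 1, footnote 14): "Patients will be provided with a device at the Screening visit to be worn for at least 7 days prior to Baseline/Day 1".
- **Screening length.** Same Synopsis section: "The study will involve a Screening period (a minimum of 7 days, up to 21 days"; Table 1, footnote 1 agrees. A 7-day Screening is therefore permitted.
- **Day numbering.** SAP 4.2.9 makes the first-dose day Day 1 and continues: "The preceding day is Day -1, the day before that is Day -2, etc". There is no Day 0.
- **Baseline window.** SAP Table 2 sets the step baseline at Day -7 to Day -1, and the observations in the window are averaged.
- **Valid days.** SAP 4.2.8: "patients need to have at least 3 of 7 daily values in a given week to provide a robust assessment of activity". It adds: "The denominator used for calculating means will be the total number of days in which steps per day is non-missing".
- **Low-count rule.** SAP 4.9.3: "Values of <1000 will be set to missing since they were considered invalid upon review of the data". The text does not say whether this acts on daily counts or weekly means.
- **Responder.** SAP 4.9.3 requires at least a 10% "increase in weekly mean steps per day from baseline at a given visit".

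No rule excludes the day of issue, and none sets a minimum wear time for a day to count.

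**The concern.** If Screening is exactly 7 days, the first day in the baseline window is the day the patient received the device. The count for that day covers only the hours after the visit, but it enters the mean with the weight of a full day. No post-dose week contains an issue day, so the error sits in the baseline alone and pulls it down.

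An understated baseline inflates every weekly change from baseline in the affected patients and raises their chance of being called step responders. The study has one arm, so there is no control group in which the same error would cancel. SAP 4.3 also allows interim results on exploratory endpoints to be published or presented.

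**Working it through.** **1. Where the issue day falls.** Counting back from Day 1 with no Day 0, 1 day before dosing is Day -1, 7 days before is Day -7, and 8 days before is Day -8. The window from Day -7 to Day -1 holds 7 calendar days, matching Table 2. Issue at a 7-day Screening is inside it; issue at 8 to 21 days is outside, and the artefact is then zero.

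**2. Size of the false rise.** Let *n* be the number of valid baseline days including the issue day, and *f* the issue-day count as a fraction of a normal day. The documents do not give *f*, so a range is shown. With no true change, the baseline is multiplied by (n - 1 + f)/n and the apparent rise is n/(n - 1 + f) - 1.

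| n | f = 0.3 | f = 0.5 | f = 0.7 |
|---|---|---|---|
| 7 | 7/6.3 - 1 = 11.1% | 7/6.5 - 1 = 7.7% | 7/6.7 - 1 = 4.5% |
| 3 (SAP minimum) | 3/2.3 - 1 = 30.4% | 3/2.5 - 1 = 20.0% | 3/2.7 - 1 = 11.1% |

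The second row is an extreme: it needs a 7-day Screening, only 3 valid baseline days, and the issue day among those 3.

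**3. When the part-day alone makes a responder.** Setting n/(n - 1 + f) = 1.10 gives f = n/1.1 - (n - 1). For n = 7, f = 6.364 - 6 = 0.364. Above about 36% of a normal day, the patient also needs some true or chance increase. With a half-day that increase is 1.10 × 6.5/7 - 1 = 2.1%.

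**4. Effect of the below-1000 rule.** If it acts on daily counts, it removes the shortest part-days. For an assumed usual 5000 steps per day the smallest fraction kept is 1000/5000 = 0.2, so the false rise with n = 7 is at most 7/6.2 - 1 = 12.9%. At 2750 steps per day the maximum is 10.0%. A half-day of 2500 out of 5000 steps is kept. If the rule acts on weekly means, it gives almost no protection.

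**5. Responder probability in affected patients.** Assume no true change, n = 7, and a log SD of 0.2 for the ratio of week to baseline (not in the documents). Then P = 1 - Φ((ln 1.10 - ln(7/(6 + f)))/0.2).

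- No part-day: 1 - Φ(0.477) = 32%
- f = 0.3: 52%
- f = 0.5: 46%
- f = 0.7: 40%

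The increases are about 20, 14 and 8 percentage points. A simulation on different assumptions (5000 steps per day, log SD 0.35 within and between patients, f uniform from 0.2 to 0.8, daily below-1000 rule applied) moved the rate from 30.8% to 42.7%, the same direction and a similar size.

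**6. Whole group.** The share with exactly 7 days of Screening is not given. If Screening lengths were uniform over the 15 values from 7 to 21 days, it would be 1/15, and the increases in step 5 become 20.3/15 = 1.4, 14.1/15 = 0.9 and 8.2/15 = 0.5 points. The simulation at the same share moved the rate from 30.9% to 31.8% and mean change by about 20 steps per day. As the share approaches 100%, the increase approaches the full 8 to 20 points.

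**The case against.** The strongest objection is scope. Only the shortest permitted Screening is affected, and at a share of 1/15 the whole-group effect is about one percentage point. That stands, and it rules out reading the issue as a general false rise in steps.

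A reader might infer that the part-day by itself manufactures responders. With 7 valid days it does so only when the fraction is about 36% or less; a half-day gives 7.7%, under the threshold. Otherwise it tips patients already close to 10%. Under the assumptions above, 32% would be responders with no change and no part-day, so most false responders come from threshold and noise.

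A reader might also infer that the protocol breaks its own rule on 7 days of wear. The text does not say full days. Day -7 to Day -1 is seven calendar days, so the wording can be met. If full days were intended, issue by Day -8 would be needed, and the 7-day Screening minimum does not enforce that. Either way the documents do not establish a contradiction.

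A third tempting inference is that the correlations of step change with WOMAC or KOOS change are pushed towards benefit. A downward baseline shift in a subset, unrelated to those scores, mainly adds noise.

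Two lesser points also stand. Advice to limit activity for 24 to 48 hours after injection (protocol 7.5.8) lowers Week 1 steps and acts against the bias, but not in later weeks. And the planned listing of steps and contributing days per patient helps a reviewer see the data, though it does not correct the mean.

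**Conclusion.** The point holds for patients screened exactly 7 days before dosing, and only for them. Their step baseline contains a part-day weighted as a whole day, so their change from baseline and their chance of meeting the responder rule are inflated. With 7 valid days the false rise is 4.5% to 11.1% for an assumed part-day fraction of 70% down to 30%.

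The group-level effect depends on an unknown share of patients. Under the log SD of 0.2, it runs from about 0.5 to 1.4 points on the responder rate at 1/15, to about 8 to 20 points if nearly everyone had a 7-day Screening. The documents do not support a claim that the study's step results as a whole are spuriously positive. The endpoint is exploratory, SAP 4.9.3 specifies no hypothesis test of step change, and the primary safety objective is untouched. This is a minor correction, worth making because the error is systematic and simple to remove.

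**What to change.** In SAP 4.2.9 and Table 2, exclude the calendar day of device issue (the Screening visit date) from the step baseline. Where Screening was exactly 7 days, the baseline becomes Day -6 to Day -1; for everyone else it stays Day -7 to Day -1. Keep the 3-valid-day minimum, which six remaining days can still satisfy. The artefact then becomes zero.

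The cost is one sentence in the SAP and one programming condition on a date already collected. The downside is the loss of at most one baseline day per affected patient; someone with exactly 3 valid days, one of them the issue day, would no longer have a valid baseline. It would help to state in the same edit whether the below-1000 rule applies to daily counts or weekly means.
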